## 7 STUDY OBJECTIVES

The primary objective is to continue to investigate the safety of lofexidine when administered for at least 7 days at clinically relevant doses (3.2 or 2.4 mg/day) to alleviate symptoms of acute withdrawal from opioids in a variety of clinical scenarios in both in-clinic and outpatient settings. The effectiveness of lofexidine is also of interest.

## 8 STUDY SPONSOR

This study will be conducted under an Investigational New Drug (IND) application (#47,857) held by US WorldMeds, LLC.

## 9 STUDY SITES AND INVESTIGATORS

This study will be conducted at approximately 20 study sites in the US. It is the responsibility of the Principal Investigators to make sure this protocol is conducted in full conformance with the ethical principles detailed in Section 16 of this protocol. All data will be collected at the study sites on source documents and entered at the site into electronic case report forms (eCRFs) as described in Section 18.1 of this protocol.

## 10 INVESTIGATIONAL PLAN

### 10.1 Overall Design

This is a Phase 3, multicenter, open-label study to evaluate the safety and effectiveness of lofexidine in alleviation of withdrawal signs and symptoms in subjects undergoing abstinence from any opioid, including methadone and buprenorphine maintenance treatment, which would likely require at least 7 days of lofexidine treatment for alleviation of withdrawal. Any subject seeking treatment for partial or total opioid withdrawal will be eligible. This can include a variety of clinical situations where opioid withdrawal illness is likely to occur, such as (but not limited to) abrupt and total withdrawal (including from methadone and buprenorphine), agonist-assisted total withdrawal, dose reduction of maintenance treatment (e.g., methadone, buprenorphine), and transition from an opioid agonist to naltrexone or buprenorphine maintenance. Subjects will be evaluated for their compliance with protocol inclusion/exclusion criteria during a screening period, lasting up to 9 days. Approximately 250 to 500 subjects will receive lofexidine treatment for 7 days, starting at a dose of 3.2 mg daily (0.8 mg QID), with lowering of the dose allowed to 2.4 mg daily (0.6 mg QID) if required for tolerability based on the subject's individual treatment goal and response per clinical judgment of the Principal Investigator. Lofexidine administration should be initiated in concurrence with the change in opioid dose which is anticipated to elicit withdrawal symptoms (e.g., first day of dose reduction, or first day of abrupt cessation) or on the first day of emergence/anticipated emergence of such symptoms as determined at the Investigator's discretion. Details regarding the timing of lofexidine therapy initiation relative to change in opioid dose and onset/expected onset of symptoms should be captured in the source. All subjects will receive all 4 doses of lofexidine in a clinic setting for the first 3 days (Days 1-3) and then, per clinical judgment of the Principal Investigator, subjects can continue to receive lofexidine doses in a clinic setting or can be treated outside of the clinic (outpatient) for the remaining 4 days of mandatory lofexidine

treatment (Days 4-7). Per Principal Investigator judgment, subjects can continue lofexidine treatment beyond Day 7 on an outpatient basis only for up to an additional 7 days (Days 8-14). Note that lofexidine dosing may be stopped at any time during Days 8-14. No subject will receive lofexidine for more than 14 days total. All subjects receiving lofexidine treatment on an outpatient basis will be required to take a dose of lofexidine in the clinic at each daily clinic visit, with required clinical assessments performed before and after dosing as listed in [Table 1](#) of Section 15. Also during outpatient treatment, subjects will be required to undergo qualitative urine drug screening at each clinic visit.

## **10.2 Number of Subjects**

The total enrollment in this study will depend on subject drop-out rates in this protocol. Enrollment will continue until a minimum total of 300 subjects (across this protocol and earlier lofexidine clinical studies expected to meet FDA safety database requirements) have been treated with clinically relevant doses of lofexidine for a minimum of 7 days. It is estimated that approximately 250 to 500 subjects will be enrolled in this open-label study in order to accrue a sufficiently large safety database for evaluation.

## **10.3 Duration of Study**

This study will be initiated after completion of the companion study, USWM-LX1-3003-1. The maximum duration of participation for each subject in USWM-LX1-3003-2 will be 23 days, including the Screening period, which can last up to 9 days, followed by up to 14 days of treatment with lofexidine.

The study will be terminated when the database is judged to be sufficient, i.e., a minimum of 300 subjects (across this protocol and earlier lofexidine clinical studies expected to meet FDA safety database requirements) have been treated with clinically relevant doses of lofexidine for a minimum of 7 days. Enrollment is anticipated to take 4 to 10 months to achieve, with the total clinical duration of USWM-LX1-3003-2 anticipated to be 8 to 12 months.

## **10.4 Dose Hold and Discontinuation Criteria (2 of 3 Rule)**

When a blood pressure, heart rate, or QTcF interval value meets criteria for withholding a dose (Section 13.2.2) or discontinuation from the study (Section 13.2.3), the value needs to be confirmed by the site personnel by repeating the vital sign measurement or ECG recording, approximately 10 to 15 minutes later. If the value is confirmed by the second measurement, the appropriate action will be taken (dose hold or study discontinuation) and the confirmatory value will be recorded in the subject's source document and appropriate eCRF. If the second value does not meet the specified criteria, a third measurement will be taken approximately 10 to 15 minutes later. If this value is confirmatory, the appropriate action will be taken (dose hold or study discontinuation) and the last confirmatory value will be recorded in the subject's source document and appropriate eCRF. If the third value does not confirm the initial finding, then no action should be taken and the third value should be entered in the subject's source and appropriate eCRF. Note that should a second or third measurement be required with waiting between measurements, the timing of the

measurement will not be considered a protocol deviation (i.e., outside the protocol-specified window).

Whenever blood pressure, heart rate, or QTcF interval values meet dose hold or study discontinuation criteria, these are to be recorded on the subject's eCRF as an adverse event (AE) or serious adverse event (SAE), as applicable. Examples are:

Item	Record Adverse Event of:
Resting Vital Signs	
SBP <90 mmHg and >20% below screen value	Hypotension
DBP <50 mmHg and >20% below screen value	Hypotension
Pulse <50 bpm and >20% below screen value	Bradycardia
Orthostatic Vital Signs	
SBP >25% below recumbent values	Postural hypotension
DBP <25% below recumbent values	Postural hypotension
Pulse >25% below recumbent values	Postural bradycardia

DBP = diastolic blood pressure, SBP = systolic blood pressure

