#### Orthostatic (after standing for 3 minutes)

- Systolic blood pressure diastolic blood pressure, or pulse >25% below recumbent values.

During outpatient treatment, if the subject experiences symptoms of hypotension and/or bradycardia (see below), he/she should call the study site and the site should instruct the subject on whether the next dose should be delayed, skipped, or he/she should be seen in the clinic. The subject should record this information in the subject diary (Appendix 3).

- marked dizziness
- fainting (especially when standing from a sitting or lying position)
- light headedness
- Fatigue
- Weakness
- shortness of breath
- chest pains
- easily tiring during physical activity
- confusion or memory problems
- blurred vision
- nausea
- cold, clammy pale skin
- rapid shallow breathing
- depression
- thirst

All instances of dose-holds must be clearly documented in the subject's source document and dosing eCRF, and the event causing the dose hold should be recorded on the AE or SAE eCRF, as applicable.

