### 13.2.3 Discontinuation Criteria

A subject will be discontinued from the study if any of the criteria listed below are met (see Section 10.4 for details on repeat confirmatory requirements). All instances should be recorded in the subject's source document and AE or SAE eCRF, as applicable.

- Resting systolic blood pressure <70 mmHg;
- Resting diastolic blood pressure <40 mmHg;
- Resting pulse <40 bpm;
- QTcF >500 msec or >25% above screen value for both males and females; or
- Syncope.

Additional discontinuation criteria based on cardiovascular events are:

- New onset of clinically significant abnormal ECG per Investigator judgment (e.g., second or third degree heart block or uncontrolled arrhythmia, prolonged QTcF interval).
- Persistent symptomatic hypotension (e.g., hypotension not responding to bed rest or fluids).
- Single occurrence of symptomatic bradycardia (as assessed by Principal Investigator/study physician/assigned staff, regardless of blood pressure) associated with chest pain, shortness of breath, or decreased level of consciousness.
- Persistent hypertension – resting blood pressure  $\geq 185/110$  mmHg recorded on 3 separate occasions taken at least 5 minutes apart AND within a 1-hour time period. If 2 of 3 readings are  $\geq 185/110$  mmHg (either systolic  $\geq 185$  mmHg or diastolic  $\geq 110$  mmHg) the subject must be discontinued.
- Medical Intervention for Cardiovascular Event: Any medical intervention (nonmedication or medication inclusive) used for the treatment of any cardiovascular event, with the exception of a positional intervention in subjects displaying hypotension.
- Any other clinically significant cardiovascular signs or symptoms that would place the subject at risk.
- Subject misses more than a total of 6 doses during Days 1-7.

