### 15.3.2 Days 4-7 (In-clinic/Outpatient)

The assessments or procedures listed below will be performed daily (unless otherwise specified) on Days 4-7 (see Section [15.3.4](#) for assessments/procedures required for discontinuation from the study).

- Study medication administration QID at 8 AM, 1 PM, 6 PM, and 11 PM. Note that if subject is receiving outpatient treatment, he/she is required to take a dose of lofexidine in the clinic at each daily clinic visit.
- SOWS-Gossop 3.5 hours after the first daily dose during in-clinic treatment; once daily before an in-clinic dose of lofexidine during outpatient treatment.
- COWS 3.5 hours after the first daily dose during in-clinic treatment; once daily before an in-clinic dose of lofexidine during outpatient treatment.

- Completion of pre-defined withdrawal treatment goal (e.g., planned detoxification/transition) as assessed by the Principal Investigator (after completion of the SOWS-Gossop and COWS).
- Concomitant medication assessment.
- Pill count and review of subject diary ([Appendix 3](#)) to measure compliance with previous day's doses if being treated as an outpatient.
- Vital signs including blood pressure and pulse at rest (sitting [or recumbent if necessary because of an AE]) and standing (if able) during in-clinic treatment before every dose and 3.5 hours after administration of study medication at 8 AM, 1 PM, and 6 PM (7 times per day); respiration and temperature before 8 AM dose only.
- Vital Signs including blood pressure and pulse at rest (sitting [or recumbent if necessary because of an AE]) and standing (if able) during outpatient treatment before an in-clinic dose of lofexidine each day and 3.5 hours after dosing. Note that if the subject cannot stay in the clinic for measurement of the 3.5-hour post-dose vital signs required on Days 4-7, they will be given a portable digital blood pressure machine for measurement of their vital signs at this required time point. Subjects will also be provided a diary ([Appendix 3](#)) to record the measurements along with any symptoms of hypotension and/or bradycardia (see list in Section [13.2.2](#)) the subject may have experienced.
- A fingerprick blood sample will be collected during outpatient treatment when the subject reports to the clinic each day (before next scheduled dose) for analysis of plasma lofexidine concentration to monitor compliance.
- AE assessment.
- Clinical laboratory tests as clinically warranted.

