### **15.3.3 Days 8-14 (Outpatient Only)**

Study medication is optional on Days 8-14 for subjects continuing to have withdrawal symptoms per the Principal Investigator's judgment. The assessments and procedures listed

below will be performed daily (unless otherwise specified) (see Section 15.3.4 for assessments/procedures required for discontinuation from the study).

- Daily clinic visits and completion of subject diary.
- SOWS-Gossop before an in-clinic dose of lofexidine.
- COWS before an in-clinic dose of lofexidine.
- Completion of pre-defined withdrawal treatment goal (e.g., planned detoxification/transition) as assessed by the Principal Investigator (after completion of the SOWS-Gossop and COWS).
- Concomitant medication assessment.
- Pill count and review of subject diary ([Appendix 3](#)) to measure compliance with previous day's doses.
- Vital Signs, including blood pressure and pulse at rest (sitting [or recumbent if necessary because of an AE]) and standing (if able) before an in-clinic dose of lofexidine and 3.5 hours after dosing on Days 8-13 and once before any dose on Day 14. Note that if subjects cannot stay in the clinic for measurement of the 3.5-hour post-dose vital signs required on Days 8-13, they will be given a portable digital blood pressure machine for measurement of their vital signs at this required time point. Subjects will also be provided a diary ([Appendix 3](#)) to record the measurements along with any symptoms of hypotension and/or bradycardia (see list in Section 13.2.2) the subject may have experienced.
- AE assessment.
- Clinical laboratory tests as clinically warranted.
- Complete physical examination as clinically warranted.
- C-SSRS (Since Last Visit Version; [Appendix 6](#)) before an in-clinic dose of lofexidine.
- A fingerprick blood sample will be collected during outpatient treatment when the subject reports to the clinic each day (before next scheduled dose) for analysis of plasma lofexidine concentration to monitor compliance.
- Qualitative urine drug screening (by on-site use of "dipsticks") will be done every day in an outpatient setting to monitor for illicit drug use.

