#### **15.5.2 Vital Signs**

Vital signs (sitting/standing systolic and diastolic blood pressure, pulse) will be measured at screening for all subjects.

During in-clinic treatment (Days 1-3 mandatory; Days 4-7 if subject receives all lofexidine doses in the clinic), resting (sitting [or recumbent if necessary because of an AE]) and standing (if able) systolic and diastolic blood pressure and pulse will be measured within 30 minutes before every dose and 3.5 hours ( $\pm 15$  minutes) after administration of study medication at 8 AM, 1 PM, and 6 PM; oral temperature and respiration before 8 AM dose only.

During outpatient treatment (Days 4-14) resting (sitting [or recumbent if necessary because of an AE]) and standing (if able) systolic and diastolic blood pressure and pulse will be measured before an in-clinic dose of lofexidine and 3.5 hours ( $\pm 30$  minutes) after dosing on Days 4-13 and once before any dose on Day 14. If the subject cannot stay in the clinic for measurement of the 3.5-hour post-dose vital signs required on Days 4-13, they will be given a portable digital blood pressure machine for measurement of their vital signs at this required time point and the values will be recorded in a subject diary ([Appendix 3](#)).

For the orthostatic vital sign (i.e., blood pressure and pulse) readings, subjects will remain at rest for 3 minutes before a vital sign reading, and then stand for 3 minutes before a second vital sign reading is taken. If a subject demonstrates potentially clinically significant vital signs (whether pre- or post-dose), as per the pre-defined criteria detailed in Sections [13.2.2](#) and [13.2.3](#), the event should be recorded on the subject's eCRF as an AE or SAE (see Sections [15.5.1](#), [16.7](#), and [16.8](#)) and the subject should be followed until medically stabilized to the satisfaction of the study physician.

Additionally, when the subject is experiencing blood pressure- or pulse-related symptoms (e.g., lightheaded, dizziness, palpitations), these should be recorded on the subject's eCRF as an AE or SAE (see Sections [15.5.1](#), [16.7](#), and [16.8](#)) even if the vital signs values do not meet the pre-defined criteria detailed in Sections [13.2.2](#) and [13.2.3](#).

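### A home blood pressure or pulse reading below a stopping limit triggers no action before the next visit if the outpatient has no symptoms

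*Protocol*

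**What the plan says.** Protocol 13.2.3 requires discontinuation at a resting systolic pressure below 70 mmHg, diastolic below 40 mmHg or pulse below 40 bpm, and adds: "see Section 10.4 for details on repeat confirmatory requirements". Section 10.4 then states that "the value needs to be confirmed by the site personnel by repeating the vital sign measurement or ECG recording, approximately 10 to 15 minutes later". Dose hold or discontinuation follows if the second or third measurement confirms the first. Otherwise: "If the third value does not confirm the initial finding, then no action should be taken and the third value should be entered".

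For outpatients, 15.3.2 makes an exception "if the subject cannot stay in the clinic for measurement of the 3.5-hour post-dose vital signs required on Days 4-7", and 15.3.3 makes the same one "if subjects cannot stay in the clinic for measurement of the 3.5-hour post-dose vital signs required on Days 8-13". Section 15.5.2 covers Days 4-13 together: "they will be given a portable digital blood pressure machine for measurement of their vital signs at this required time point". The values go into the subject diary.

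The outpatient safety instruction in 13.2.2 reads: "if the subject experiences symptoms of hypotension and/or bradycardia (see below), he/she should call the study site". Sections 13.3 and 15.5.1 give similar instructions, also triggered by symptoms. The numeric dose-hold criteria in 13.2.2 apply to pre-dose vital signs.

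**The concern.** The 3.5-hour reading is taken at what 15.3.1 gives as the estimated time of maximum plasma concentration, so it is well placed to show a low blood pressure or pulse. When it is taken at home, the step that 10.4 requires before any action cannot be carried out, because no staff member is present to repeat it. Nothing in the supplied text puts another step in its place.

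A subject without symptoms has no instruction to call, and the site need not know of the value until the next visit. Until then the subject goes on dosing below a threshold that the protocol itself sets for stopping the drug. The primary objective is safety in both in-clinic and outpatient settings, so this lies within what the study is meant to watch.

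**Working it through.** The plan gives no figure for this point, so the check compares the sections and then counts scheduled doses.

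**Does any rule reach an asymptomatic home value before the next visit?**

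- 10.4: action follows confirmation by site personnel 10 to 15 minutes later. This cannot be done for a reading taken away from the site.
- 13.2.2 dose hold: uses pre-dose values. An outpatient's only scheduled pre-dose reading is before the one in-clinic dose each day, so the hold does not cover a 3.5-hour post-dose value.
- 13.2.2, 13.3 and 15.5.1 instructions to call or delay: triggered by symptoms only.
- 15.5.2: values outside the limits, pre- or post-dose, are recorded as adverse events and followed. No deadline is set, and no route is given for a home value to reach the site.
- 14.5.1: the investigator must discontinue a subject whose vital signs meet 13.2.3. It does not say how or when the site learns of a home value.
- 15.3.2 and 15.3.3: the diary is reviewed at visits, to check compliance with the previous day's doses.

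None of these requires action before the next visit.

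**Does the next staff reading replace the repeat?** It is taken before the in-clinic dose. At an 8 AM visit that is 9 hours after the 11 PM dose, compared with 3.5 hours after a dose for the home reading. A normal value then does not refute the earlier low.

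**How much drug could be taken in between?** Inputs: doses at 8 AM, 1 PM, 6 PM and 11 PM (13.2.1); 0.6 or 0.8 mg per dose on Days 4-6; and visit times that may run from one morning to the next afternoon (12.2). The home reading falls at the clinic dose time plus 3.5 hours. The amount taken is the number of doses before the next visit times the dose.

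| Clinic dose | Home reading | Next visit | Doses before visit | Gap | Amount at 0.6 to 0.8 mg |
|---|---|---|---|---|---|
| 1 PM | 4:30 PM | 8 AM | 6 PM, 11 PM (2) | 15.5 h | 2 × 0.6 = 1.2 mg to 2 × 0.8 = 1.6 mg |
| 8 AM | 11:30 AM | 8 AM | 1 PM, 6 PM, 11 PM (3) | 20.5 h | 3 × 0.6 = 1.8 mg to 3 × 0.8 = 2.4 mg |
| 8 AM | 11:30 AM | 1 PM | 1 PM, 6 PM, 11 PM, 8 AM (4) | 25.5 h | 4 × 0.6 = 2.4 mg to 4 × 0.8 = 3.2 mg |

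On the Day 8-13 taper the amounts are smaller. A subject treated as an outpatient from Day 4 through Day 13 who could never stay would have 10 home readings. These figures show opportunity, not frequency.

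**The case against.** The strongest objection is that the point rests on text nobody here has seen. Appendix 3 is where home readings are written down, and a line telling the subject to call below a given value would naturally sit there. The site file binder (16.1) and site training (16.6.2) could carry the same instruction. This stands as a limit on the conclusion. It does not remove the problem in 10.4, which has no wording for a reading that staff cannot repeat.

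The exposed group is also narrow. Under 13.2.1 the decision to allow outpatient care should weigh hypotensive sensitivity seen over Days 1-3, when staff take 7 vital-sign sets a day, 7 × 3 = 21 in all. Home measurement is only for those who cannot stay. The 13.2.2 symptom list has 15 items, including fatigue, nausea and thirst, which many people in opioid withdrawal would report. This bears on frequency and stands. It does not help the subject who has a low value and no symptoms, whom a scheduled numeric reading is there to find.

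Against the fix, one can say that stopping on a single self-reading is stricter than the clinic rule, under which two normal repeats mean no action. But the fix is a pause pending a call, not a discontinuation. Section 15.5.1 already asks symptomatic outpatients to delay dosing until told otherwise, and the 2-of-3 confirmation stays with staff.

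**Conclusion.** The point holds. On the supplied text, an asymptomatic home reading below a 13.2.3 blood pressure or pulse limit requires no action before the next daily visit, and two to four further doses can be taken over 15.5 to 25.5 hours.

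The conclusion assumes that Appendix 3 and the site instructions contain no numeric rule for calling or holding a dose; if they do, the remaining gap is the wording of 10.4. The dose counts assume the prescribed schedule and the visit times in the table. The documents give no rate of home measurement or of limit crossings, so the number of subjects affected cannot be estimated. It is probably small. The change should be made because the exposure concerns the protocol's own stopping limits and the remedy is cheap. Confidence is medium, mainly because the diary was not available.

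**What to change.** Add to 10.4 and 15.5.2, and to the diary if it is not already there:

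- A subject whose home reading meets a 13.2.3 blood pressure or pulse limit takes no further dose and calls the site at once, with or without symptoms.
- The subject may repeat the reading after 10 to 15 minutes to inform the call, but normal self-repeats do not cancel it.
- The site decides on a hold, a same-day visit or discontinuation. Staff carry out the 2-of-3 confirmation.

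A home/clinic flag in the vital-signs listing is optional.

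The cost is wording in two sections and the diary, plus some extra calls, held doses and occasional same-day visits from falsely low home readings. One side effect needs watching. Section 13.2.3 also discontinues on this criterion: "Subject misses more than a total of 6 doses during Days 1-7". It does not say whether a held dose counts as missed. If it does, false lows on Days 4-7 would use up part of that allowance, so the site should resolve each call promptly.
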